benefit obtained when both are used together.^{50,52-53} The combination of exercise and plasticity-based CT has not been previously tested in HF or in other populations as an intervention for improving cognitive outcomes,^{50,64-66} but may be most optimal for targeting the underlying mechanisms for CI in HF. The proposed feasibility study is designed to test the acceptability, implementation and limited efficacy of a combined exercise (Ex) and cognitive training (CT) intervention in stable NYHA class II and III heart failure patients with cognitive impairment. A total of 60 participants will be randomized to one of three study arms: Ex/CT (N=20), Ex-alone (N=20), and attention control (N=20). The study aims are:

Aim 1: To evaluate the feasibility of a 3-arm intervention (ExCT, Ex, AC) in heart failure patients with CI.

Aim 1a. To test the acceptability and implementation of each study arm.

Aim 2: To ascertain limited efficacy of the 3-arm intervention on changes in cognitive abilities

Aim 3: To ascertain limited efficacy of the 3-arm intervention to improve cerebral oxygenation, physiological status, physical function and QOL.

A. Significance. Approximately 670,000 individuals are diagnosed with HF annually in the United States,⁶⁷⁻⁷⁰ and over one million hospitalizations occur each year due to HF, especially among adults 65 years of age and older.⁷¹⁻⁷³ As many as 60% of persons with HF experience cognitive impairment, (CI); this number increases proportionately as HF worsens.^{5-6,10,74-76} Increased age and depression are independent predictors of more severe CI in persons with HF.^{5-6,77-82} CI often interferes with the ability to engage in effective self-management of HF; this leads to more frequent hospitalizations and contributes to the cost burden on the health care system and reduced quality of life.^{6,74-75,83} To reduce these burdens, we propose a nurse-led exercise and cognitive training intervention that targets underlying mechanisms that contribute to CI in persons with HF.

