B. Innovation: Available evidence to guide care for persons with HF who are cognitively impaired is nonexistent. Our preliminary work using exercise and cognitive behavioral strategies⁹⁴⁻¹⁰⁰ has shown improved physical, psychological and QOL outcomes in persons with HF. The proposed study will expand this work and provide important insight on an innovative intervention strategy (exercise and CT) and novel biomarkers (BDNF, cerebral oxygenation) in a diverse population of HF with CI. No study has documented whether exercise improves cerebral oxygenation in persons with HF; the one study measuring cerebral oxygenation in persons with HF found a significantly reduced cerebral oxygenation level using near infrared spectography (NIRS), despite a normal peripheral oxygen saturation.¹⁰¹ Combination physical exercise and cognitive training have never been evaluated in HF to improve CI. This dual process may provide a synergistic, additive benefit through different yet complementary mechanisms of recovery. This feasibility study will provide essential information to optimize the potential success of a future, large scale research trial.

C. APPROACH.

Design. A pre-post randomized controlled design will be used to measure study aims. Sixty participants will be randomized to receive ExCT (N=25), Ex-alone (N=25), or attention control (N=25) intervention conditions for 3 months. Assessments will take place at baseline, intervention completion (3-months) and 6 months post-intervention. Outcomes of interest include cognitive functioning, peak oxygen consumption (peak V_O₂), BDNF, and Kansas City Cardiomyopathy Questionnaire (KCCQ; HF specific quality of life instrument). After a 4-5 month start-up for hiring and training, enrollment will begin. Recruitment/enrollment will take place over 18 months; the final follow-up appointment in month 30. This will leave 6 months for data analysis and dissemination.

Outcomes of interest include cognitive functioning, peak oxygen consumption (peak V_O₂), BDNF, and Kansas City Cardiomyopathy Questionnaire (KCCQ; HF specific quality of life instrument). After a 4-5 month start-up for hiring and training, enrollment will begin. Recruitment/enrollment will take place over 18 months; the final follow-up appointment in month 30. This will leave 6 months for data analysis and dissemination.

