Sociodemographic and clinical variables will be obtained from self-report and medical records. The Charlson Comorbidity Index (CMI)¹⁰⁸ will quantify the cumulative risk of death. **Mini Mental Status Examination**¹⁰² will be used to screen for study inclusion for mild to moderate cognitive impairment (score of 20 for 8-9 yrs of schooling; 22 for 10-12 yrs of schooling; 23 for >12 yrs)¹⁰² and has excellent specificity at this cut-off point.⁵

The **Beck Depression Inventory-II** (BDI-II)¹⁰⁹ has been widely used in the HF population. Scores will be used as an effect modifier and explored as a potential outcome variable. **Cognitive Function.** We will use the

Center’s core neuropsychological testing battery of well-established and validated instruments that are described in the Biobehavior and Methods Core (BMC) portion of this application. The BMC will provide training on test administration and scoring and will aid in data management and interpretation. Cerebral tissue oxygenation will be assessed in the CIN by a cerebral oximeter sensor (Casmed, Blanton, CT) using near infrared spectrography (NIRS). NIRS is widely used and validated in a variety of fields to assess cerebral tissue oxygenation.^{86,101}

Table 3. Variables, measures, instruments and time of evaluation

Variable	Measure/Instrument	# of items/time	Time of Evaluation
Antecedents Participant Demographics & Clinical information: Co-morbidity, Cardiac Fx, Meds	Age, gender, education, marital status, Charlson comorbidity Index (CMI) LVEF, NYHA class, length of time with HF & etiology, Medications	Chart review & questionnaire Questionnaire	Baseline (BL)
Mild-moderate cognitive impairment	MMSE	30 item/10 minutes	BL only
Depressive symptoms	BDI-II	21 item/15 minutes	BL only
Cognitive function	Repeatable Battery for the Assessment of Neuropsychological Status (RBANS) Controlled Oral Word Association Test Color Trails 1 & 2 WAIS-III Digit Span/Letter Number Sequence Stroop Test Ruff 2 & 7 Test Rey Auditory Verbal Learning Test	30 minutes 5 minutes 10 minutes 10 minutes 5 minutes 5 minutes 10 minutes	BL, 3 and 6 months

Physical function	Peak oxygen consumption (Modified Balke)	20 minutes	BL & 3 mos
Physiological status	BDNF	NA	BL & 3 mos
Cerebral oxygenation	Near infrared spectography,	30 minutes	BL & 3 mos
Quality of Life	KCCQ	23 items /15 minutes	BL, 3 and 6 months

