Procedures Recruitment, Screening and Enrollment of participants will occur through physician and other health care provider referrals and patient self-referral. These methods have proved successful in our prior work. The recruitment nurse will arrange a time for laboratory, and treadmill tests at the CIN. Baseline (T1) measures will be taken in the CIN by a trained data collector blinded to group assignment. All participants will be given the same measures, in the same sequence at each time point. Questionnaire completion should take 30 minutes or less, the neuropsychological testing is anticipated to take 75 minutes. Laboratory samples will be taken prior to the treadmill test. The BDNF samples will be stored at -80 in the CIN until processed. After the laboratory work is completed, the modified Balke treadmill test will be conducted by an exercise physiologist; emergency equipment, doctors and nurses are available. After BL, participants will be randomized to study groups by computerized sheet prepared by the study statistician. At 3 and 6 months we will follow the same procedures used at Evaluation 1. After Evaluation 3, participants will be discharged from the study, and all participants provided with study results. A \$50 honorarium will be provided at each measurement time point, to total \$150/patient for completing the study. Intervention process measures (evaluation, attendance) will be tracked and evaluated to maintain internal validity. Protocol adherence will be calculated for both groups.

Data Management and Analysis. The Biobehavioral and Methods Core (BMC) will coordinate the collection, integration, and analysis of biological and psychosocial data for this study. Data will be analyzed using both descriptive and inferential test statistics. We will build multivariable statistical models to examine the relationship between an Ex/CT intervention to exercise alone and attention control (AC) on cognitive functioning (P-30 Neuropsychological Battery), cerebral oxygenation (NIRS, 3 months only), physiological status (BDNF), physical function (peak VO_2) and QOL (KCCQ) in HF at BL, 3 and 6 months controlling for but not limited to age, gender, SES, depression, social support, NYHA class, medications and comorbidities.

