Since the intent of this study is exploratory; hypothesis testing will not be the primary focus of the statistical analysis. Rather, we will analyze data with the specific intent of establishing population parameters (e.g., effects sizes) for the variables being investigated. Confidence intervals will be calculated for all effect sizes associated with the predictor variables, other significant outcome effects, and for changes over time. These effect size estimates will be used to design the future R01 study. Given the relatively small sample size of $n=60$ at 80% power, and $\alpha=.05$, we will have the ability to detect a moderate ($d=.5$) to large effect size ($d=.8$). We will use

general linear and/or mixed models as the main modeling framework for analyses of the outcome measures in the projects. We will build full factorial models to test for interactions and review estimated marginal means. We will use Using G*Power 3, to estimate actual power for the GLM analysis both a priori and post hoc.

E. HUMAN SUBJECTS RESEARCH

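### Neither the arm contrast nor the use of each outcome's own baseline is specified; naming that baseline as a covariate would usually narrow the intervals at almost no cost

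*Combined protocol and SAP*

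**What the plan says.** - **Design:** "A pre-post randomized controlled design will be used to measure study aims".
- **Procedures:** "After BL, participants will be randomized to study groups by computerized sheet prepared by the study statistician". No stratification factor is named.
- **Table 3** ("Variables, measures, instruments and time of evaluation") schedules a baseline measurement for cognitive function, peak oxygen consumption, BDNF, cerebral oxygenation and KCCQ. All five are repeated at 3 months, and cognition and KCCQ also at 6 months.
- **Data Management and Analysis** describes multivariable models of these outcomes "at BL, 3 and 6 months controlling for but not limited to age, gender, SES, depression, social support, NYHA class, medications and comorbidities". The framework is general linear and/or mixed models, and "We will build full factorial models to test for interactions and review estimated marginal means".
- **The output** is estimation rather than testing: "Confidence intervals will be calculated for all effect sizes associated with the predictor variables, other significant outcome effects, and for changes over time".
- **The purpose** of that output is stated in the same section: "These effect size estimates will be used to design the future R01 study".

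Nowhere is an outcome's own baseline value named as an adjuster. The section does not say whether the arm effect is a difference in change, a difference at follow-up, or a baseline-adjusted difference.

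**The concern.** Listing baseline with 3 and 6 months, calling the design pre-post, testing interactions and giving intervals for changes over time together point to an arm-by-visit model in which the arm effect is a difference in change from baseline. With 20 or 25 per arm, that contrast usually gives up precision that the scheduled data could supply.

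The listed adjusters do not make up for this. Fixed traits such as age and gender, entered as main effects, cancel out of a within-person change contrast.

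Baseline balance in such small arms is left to chance, and a change contrast carries part of any chance gap into the effect size, so an arm that happens to start lower tends to appear to improve more. The effect sizes and their intervals are meant to inform the design of the next trial, so both their width and their dependence on a chance gap matter.

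**Working it through.** The plan gives no figure on this point: no correlation, no SD and no interval width. Its detectable range of d = .5 to .8 is not tied to a stated contrast and is not used here.

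**Inputs**
- n per arm: 20 (Specific Aims). Design prints 25 per arm. With the 85% retention expected in Human Subjects Research, 20 × 0.85 = 17. Three arms, so N = 3n.
- rho: not in the documents; assumed .5, .7 and .8, with .9 also shown.
- Ratio k of follow-up SD to baseline SD: not in the documents; assumed 1, with 1.2 and 1.3 as a sensitivity check.

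**Formulas** for one pairwise contrast, in baseline SD units
- Change: variance = (1 + k² − 2·rho·k) × 2/n, with t on N − 3 df.
- Baseline-adjusted: variance = k²(1 − rho²) × 2/n × (N − 4)/(N − 5), with t on N − 4 df. The last factor is the small-sample cost of estimating the slope.
- Half-width = t × √variance.

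**Equal SDs (k = 1), n = 20.** Here t is 2.0025 on 57 df and 2.0032 on 56 df, and the inflation is 56/55 = 1.018.

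| rho | Change: variance, half-width | Adjusted: variance, half-width | Narrower by |
|---|---|---|---|
| .5 | 0.1000, 0.633 | 0.0764, 0.554 | 12.6% |
| .7 | 0.0600, 0.491 | 0.0519, 0.456 | 6.9% |
| .8 | 0.0400, 0.400 | 0.0367, 0.384 | 4.2% |
| .9 | 0.0200, 0.283 | 0.0193, 0.279 | 1.6% |

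Without the small-sample cost the ratio of standard errors is √((1 + rho)/2), giving 13.4%, 7.8% and 5.1% at rho .5, .7 and .8. A simulation of 6,000 replicates at n = 20 gave mean half-widths of 0.630 against 0.550, 0.488 against 0.454, and 0.399 against 0.382.

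**Other arm sizes.** At rho .5, .7 and .8 the gain is 12.4%, 6.8% and 4.1% with 17 per arm, and 12.8%, 7.1% and 4.4% with 25. The disagreement in the documents between 20 and 25 per arm does not affect the conclusion.

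**Mixed-model form.** With three visits, compound symmetry and complete data at n = 20, freeing the baseline means against constraining them equal gives contrast variances of 0.100 against 0.075, 0.060 against 0.051, and 0.040 against 0.036. These match the formulas before the small-sample cost.

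**Unequal SDs, n = 20**
- k = 1.2, rho .7: 0.552 (change) against 0.548 (adjusted), a gain of 0.8%.
- k = 1.2, rho .8: the change variance is (1 + 1.44 − 1.92) × 0.1 = 0.0520, half-width 0.457. The adjusted variance is 1.44 × 0.36 × 0.1 × 1.018 = 0.0528, half-width 0.460. The adjusted interval is slightly wider.
- k = 1.3, rho .7: 0.591 against 0.593, again slightly wider.

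**Chance baseline gap.** With 20 per arm the standard error of the baseline difference between two arms is √(2/20) = 0.316 SD. A gap at least that large occurs with probability 0.32 for a given pair, and 0.58 for at least one of the three pairs (studentised range, three groups). With equal SDs, given such a gap, the change contrast shifts by (1 − rho) × 0.316 = 0.16, 0.09 and 0.06 SD at rho .5, .7 and .8. The adjusted contrast shifts by 0 in expectation. For scale, the only cognitive effect the protocol gives in SD units is one third of an SD, in healthy users (Brain Fitness Computer Training).

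**Coverage.** In the simulation both methods covered at 95% overall. When the gap was at least one standard error, the change contrast covered at 91%, 93% and 93%, against 94%, 95% and 95% for the adjusted contrast.

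**The case against.** The strongest reply is that the plan has not chosen a change-score analysis. A reader might infer that it has, or that treating baseline as a visit is itself an error. The documents support neither. The adjuster list is expressly open, and either model class can take a baseline covariate. Intervals for changes over time are listed separately from those for the predictors. Interactions could refer to depression, which the measures section treats as an effect modifier. Marginal means are also standard output from a covariate-adjusted model. For cerebral oxygenation the analysis text mentions 3 months only, although Table 3 also measures it at baseline. All of this stands: the gap is one of specification, and the change contrast is only the most natural reading. If the intended contrast were instead the follow-up means ignoring baseline, the gain from adjustment, before small-sample cost, would be 1 − √(1 − rho²): 13%, 29% and 47% at rho .5, .7 and .85. The remedy would be the same.

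A second reply is that the gain is modest and conditional. That also stands. At rho .7 it is about 0.03 SD, and either interval is wider than the one-third SD benchmark. A reader might infer that adjustment loses only at extreme correlations; that needs equal SDs, which the documents do not establish, and entry restricted by MMSE cut-offs is a reason not to take them for granted. A reader might also equate the loss at rho .7 with the expected 15% attrition. It is not equal once the degree of freedom is charged: adjusted at 17 per arm gives 0.50, against 0.49 for change at 20.

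Third, Aim 1 is feasibility, so effect sizes are one output among several. True, but they are the stated input to the next trial.

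**Conclusion.** The point holds as an unspecified analysis choice with a better option available at almost no cost. It does not show bias or invalidity: across randomisations both contrasts are unbiased with 95% coverage. The 13% to 4% narrowing rests on an assumed rho of .5 to .8, equal SDs at baseline and follow-up, and a change contrast as comparator. It also leaves out the eight planned adjusters, so it indicates the size of the gain rather than the width of the plan's own intervals. The benefit that depends less on rho being moderate is protection against a chance baseline gap, which matters in arms this small. This is worth considering, and is not a defect that undermines the study.

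**What to change.** In Data Management and Analysis, state one of the following:
- each outcome's baseline value is a covariate in the model of its follow-up visits; or
- baseline stays as a modelled visit, with baseline means constrained to be equal across arms.

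Then state that the reported effect size is the adjusted arm difference at 3 months, and at 6 months where the outcome is measured, with its 95% confidence interval.

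The cost is one or two sentences and about one degree of freedom per model. No extra visit, measurement or participant is needed, and the listed adjusters can stay as they are.

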Inclusion criteria: (a) 75 outpatient men and women between the ages of 40 and 75; (b) English speaking; (c) live independently within a 60 mile radius of Atlanta; (d) meet education corrected cut-offs on the MMSE indicating cognitive impairment (score of 20 for 8-9 yrs of schooling; 22 for 10-12 yrs of schooling; 23 for >12 yrs)¹⁰²; (e) have a computer with internet connection; (f) documented medical diagnosis of NYHA class II or III systolic. (g) Left ventricular ejection fraction (LVEF) $\geq 10\%$ that is documented within the last year by echocardiogram, cardiac catheterization ventriculography or radionuclide ventriculography; (h) Receiving medication therapy for HF according to American College of Cardiology (ACC) American Heart recommendation guidelines¹⁰³ for at least 8 weeks prior to study enrollment. Exclusion criteria: a) NYHA class I or IV; (b) change in HF therapy within 8 weeks; (c) worsening HF symptoms within last 5 days; (d) unstable angina; (e) renal insufficiency (serum creatinine > 3.0 mg/dL); (f) fixed rate pacemaker; (g) uncontrolled hypertension; (h) not involved in any structured exercise program or exercising 3 or more times per week for a minimum of 30 minutes and; (i) not hospitalized within the last 30-days; (j) not diagnosed with any neurological disorder that may interfere with cognitive function; (k) Beck Depression Inventory II (BDI-II) score greater than 25; and (l) any disorder interfering with exercise participation.

It is anticipated that approximately 50% of patients approached regarding the study will be eligible and will agree to participate. Based on the PI's earlier studies, a retention rate of 85% is expected. The actual acceptance and retention rates will be included as part of the information gleaned from this feasibility study to inform the design and methods for a subsequent, large scale efficacy trial.

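### The power sentence (n=60, 80% power, d=.5 to .8) is not met at d=.5 for a pairwise arm comparison without an unstated correlation, and the protocol gives both 60 and 75 as its sample size

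*Combined protocol and SAP*

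**What the plan says.** **Power.** The Data Management and Analysis part of section C opens its power sentence with "Given the relatively small sample size of $n=60$ at 80% power", sets alpha at .05, and concludes that "we will have the ability to detect a moderate ($d=.5$) to large effect size ($d=.8"). The analysis is to use "general linear and/or mixed models as the main modeling framework", with covariate adjustment and tests of interaction. The comparison described is Ex/CT against exercise alone and against attention control. G*Power is to be run before and after the trial. No contrast, sidedness, baseline or repeated-measures correlation, or attrition allowance accompanies the d values.

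**Sample size.** Four places bear on it:

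- Specific Aims: "A total of 60 participants will be randomized to one of three study arms: Ex/CT (N=20), Ex-alone (N=20), and attention control (N=20").
- Section C, Design: "Sixty participants will be randomized to receive ExCT (N=25), Ex-alone (N=25), or attention control (N=25) intervention conditions for 3 months".
- Section C, power sentence: n=60.
- Section E, inclusion criteria: "75 outpatient men and women between the ages of 40 and 75".

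Section E adds that "a retention rate of 85% is expected", without saying at which visit.

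**The concern.** Cohen's d is a difference between two means, and the stated comparison is between arms, so the natural reading of the power sentence is a pairwise contrast. Twenty or 25 per arm looks far too few for 80% power at d=.5 on that reading. A reader would expect four chances in five of detecting a moderate effect where an unadjusted pairwise comparison has about one in three.

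The plan says its effect sizes will be used to design the later R01, so the account of what this sample can show should be reproducible. Aim 1 is feasibility, which makes the enrolment target a basic parameter, yet it is ambiguous by 75 − 60 = 15 participants.

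**Working it through.** **Inputs from the documents:** N = 60 (20 per arm) or 75 (25 per arm), power 80%, alpha .05, d = .5 and .8, retention 85%. **Assumptions, because the documents are silent:** two-sided test (one-sided also shown), SD = 1, equal arms, and any correlation.

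**1. Sample size.** 3 × 20 = 60, but 3 × 25 = 75, so the Design sentence contradicts itself. Retention does not reconcile the two figures: 75 × .85 = 63.75, not 60, and the Design sentence speaks of sixty randomised, not sixty completing. With 85% retained, 60 × .85 = 51 (17 per arm), and 75 leaves about 21 per arm. These are pessimistic cases, since a mixed model can use partial follow-up.

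**2. Trying to reproduce d=.5 to .8: unadjusted pairwise contrast.** Power comes from the noncentral t with 2n − 2 degrees of freedom and noncentrality d × √(n/2). At 20 per arm, d=.5 gives .5 × √10 = 1.58 and d=.8 gives 2.53. At 25 per arm they are 1.77 and 2.83.

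| Per arm | Power, d=.5 | Power, d=.8 | Detectable d at 80% |
|---|---|---|---|
| 20 | 34% | 69% | 0.91 |
| 25 | 41% | 79% | 0.81 |
| 17 (20 less 15%) | 29% | 62% | 0.99 |
| 21 (25 less 15%) | 35% | 72% | 0.89 |

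Taking the error degrees of freedom from all three arms (3n − 3) changes little: detectable d is 0.90 at 20 per arm and 0.80 at 25. Simulation of 200,000 trials agrees: 34% and 70% at 20 per arm, 41% and 79% at 25. One-sided, power at d=.5 is 46% and 54%, and detectable d is 0.80 and 0.71. Unadjusted, d=.5 needs 64 per arm.

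**3. Readings that put the detectable d inside .5 to .8 at N=60.**

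- *Baseline adjustment.* The variance is multiplied by 1 − r². At 20 per arm, r=.5 gives d=0.79 and r=.7 gives 0.65.
- *Both exercise arms pooled against control, 40 v 20.* The standard error is √(1/40 + 1/20) = 0.274, giving d=0.78. Power at d=.5 is 43%.
- *Baseline-adjusted mean of the two follow-ups, common correlation ρ.* The variance factor is (1 + ρ)/2 − ρ². At ρ=.5 it is 0.50, giving 0.90 × √0.50 = 0.64.

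The last is not available for "cerebral oxygenation (NIRS, 3 months only").

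**4. Correlation needed to reach d=.5 itself.** For the pairwise contrast solve (unadjusted detectable d) × √(1 − r²) = 0.5, using the three-arm degrees of freedom:

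- 20 per arm: r = √(1 − (0.5/0.901)²) = 0.83.
- 25 per arm: r = √(1 − (0.5/0.803)²) = 0.78.
- 17 per arm: 0.86.

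For the other between-arm contrasts at N=60, it is 0.77 for pooled arms, 0.76 for the two-visit mean, and 0.64 for both together. Completers needed per arm for pairwise d=.5 fall from 64 to 48 if r=.5 and 33 if r=.7 (49 and 34 with two-arm degrees of freedom).

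**The case against.** The strongest reply is that the power sentence never names a pairwise contrast. The plan's models are adjusted, longitudinal and factorial, so an unadjusted t-test at one visit is not the planned analysis. Several other readings do meet the moderate figure:

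- Pre-post change over all 60 participants has 97% power at a standardised change of .5.
- Within-arm change is detectable at 0.66 with 20 per arm.
- A group-by-time interaction of f=.25 at N=60 has 82% power with two visits and 90% with three, if the correlation is .3.
- At N=75, pooled exercise arms against control on a two-visit mean with ρ=.5 have 81% power at d=.5.

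The range .5 to .8 might also be meant loosely, as the band in which the detectable effect falls. And the plan says hypothesis testing is not its main focus.

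Much of this stands as a limit on the claim. The sentence is under-specified for those other tests, not shown to be wrong for them, and the harm is modest in an estimation study. It does not rescue the pairwise claim. The within-group figures are not differences between arms. The interaction f is an omnibus measure on another scale. The interaction and the N=75 reading each rest on a correlation that the plan does not state. None of it touches the conflict over N.

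**Conclusion.** The concern holds. For a pairwise between-arm comparison, 80% power at d=.5 is not delivered at either sample size without a baseline correlation of roughly 0.8 that appears nowhere in the documents. Unadjusted two-sided power is 34% at 20 per arm and 41% at 25. The d=.8 end also falls short at n=60 (69–70%), though it is essentially reached at 25 per arm before dropout (79–80%). These figures assume equal arms and alpha .05 without multiplicity adjustment; every correlation used is an assumption.

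The conflict over N needs no assumption: current text gives both 60 and 75, and nothing reconciles them. This should be fixed. Its consequences are confined to an irreproducible statement of what the sample can detect and an enrolment target uncertain by 15.

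**What to change.** 1. State one total and one per-arm allocation, and use it in Specific Aims, Design, the power sentence and the inclusion criteria.
2. Replace the power sentence with a figure for a named contrast and test, giving sidedness, assumed correlation and treatment of the 85% retention. For a two-sided pairwise contrast, the choices are below. Ranges run from full retention to 15% lost, and r=.7 is an assumption to be justified.

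| Allocation | Detectable d, unadjusted | Detectable d, r=.7 | 95% CI half-width, unadjusted | 95% CI half-width, r=.7 |
|---|---|---|---|---|
| 20 per arm | 0.91–0.99 | 0.65–0.71 | 0.64–0.70 SD | 0.45–0.49 SD |
| 25 per arm | 0.81–0.89 | 0.58–0.63 | 0.57–0.62 SD | 0.40–0.44 SD |

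The half-width suits the plan's stated aim of estimation better than a power figure.

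3. If G*Power is run after the trial, do not enter the observed effect. Rely on the confidence intervals already planned.

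The power change is text only, and its price is a less favourable stated figure. Settling N may move enrolment by up to 15 participants, depending on which size is actually in use.
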